O₂ saturation will be measured by pulse oximetry at every vital sign visit and if there is a clinically significant drop in O₂ saturation, this should be followed up with full pulmonary function tests (PFTs) and high resolution CT (HRCT) scan of the chest. ECGs, chest X-Ray, and O₂ saturation will be performed on patients in cases of dyspnoea or pulmonary oedema in addition to other assessments as per local standard practice.

A MUGA scan and/or echocardiogram will be performed at screening, week 3 and week 5 (+/- 1 week). Further scans are required should signs of congestive heart failure occur after this time point.

Pregnancy tests (for female pre-menopausal women) will be repeated every 8 weeks whilst on study.

Tumour assessments will be performed preferably using contrast enhanced CT or MRI (see [Appendix C](#) for assessment methods) every 8 weeks (relative to date of first dose with AZD8330) with a +/-7 day visit window.

A complete ophthalmologic examination must be performed 2 weeks prior to first dose (Day 1), and at week 5 (+/- 1 week). If a patient receiving AZD8330 experiences an AE of visual

disturbance (for example blurring of vision) a complete ophthalmologic examination including slit-lamp examination must be performed.

Following withdrawal from AZD8330 for any reason, patients will have clinical chemistry/haematology, coagulation, urinalysis, physical examination, vital signs, ECG, and AE assessments.

Following withdrawal from randomised treatment for any reason, patients may receive any subsequent therapy for their disease at the discretion of the investigator. Details of such treatment are to be recorded in the pCRF.

All patients will be followed until withdrawal of consent or the end of the study (the point at which the last patient recruited has received 6 months of treatment with AZD8330 or withdrawn from the study, whichever is sooner). Where possible, adverse events will be followed to resolution.

Patients who continue to receive treatment beyond the defined end of the study, in accordance with Section 7.6 (Study timetable and end of study) will be followed up according to the investigational site standard of care and investigator judgement. Investigators must continue to report all Serious Adverse Events to AstraZeneca Patient Safety Department until 30 days after study treatment is discontinued in accordance with Section 4.5.1.2 (Recording of adverse events) and 4.5.1.3 (Reporting of serious adverse events).

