3.1.4.2 Definition of a Dose Limiting Toxicity

A dose limiting toxicity is toxicity considered related to treatment with AZD8330, occurring in the first 35 days of treatment that is:

- Haematological
 - any CTC Grade 4 toxicity (CTC Grade 4 neutropaenia has to be present for >7 consecutive days to constitute a DLT)
 - \geq CTC Grade 3 neutropaenia with fever. Fever is defined as a temperature of $>37.5^{\circ}\text{C}$ orally, 37.2°C axillary or 38°C rectally measured

- \geq CTC Grade 3 thrombocytopenia associated with bleeding (excluding patients receiving therapeutic systemic anticoagulation)
- Any non-haematological CTC Grade 3 or 4 toxicity despite adequate supportive care that is not clearly related to underlying disease.
- Any continuous dose interruption for >2 weeks for any toxicity considered by the Investigator or AstraZeneca to be possibly related to AZD8330.
- Any toxicity that, in the opinion of the investigator, is sufficiently clinically significant to be considered a DLT.

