OAEs will be identified by the Study Delivery Team Physician in consultation with the appropriate Global Drug Safety Physician during the evaluation of safety data for the Clinical Study Report. Significant adverse events of particular clinical importance, other than SAEs and those AEs leading to discontinuation of the patient from study treatment, will be classified as OAEs. Examples of these are marked haematological and other laboratory abnormalities, and certain events that lead to intervention (other than those already classified as serious), dose reduction or significant additional treatment. For each OAE, a narrative may be written and included in the Clinical Study Report.

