It is important to distinguish between serious and severe AEs. Severity is a measure of intensity whereas seriousness is defined by the criteria in Section 4.5.1.1. An AE of severe intensity need not necessarily be considered serious. For example, nausea that persists for several hours may be considered severe nausea, but not a SAE. On the other hand, a stroke that results in only a limited degree of disability may be considered a mild stroke but would be a SAE.

AEs will be graded according to the National Cancer Institute Common Terminology Criteria for AEs (NCI CTC Version 3, June 2003).

The following variables will be collected for each AE:

- AE description
- Onset date and time
- Resolution date and time
- Changes in CTC grade
- Action taken
- Treatments patient received for AE
- Outcome
- Causality (yes or no)

- Whether event constitutes an SAE

AEs will be coded using MEDRA (Medical dictionary for regulatory activities).

After study completion (ie, after any scheduled follow-up period has ended) there is no obligation to actively report information on new AEs or SAEs occurring in former study patients. However if an investigator learns of any SAEs, including death, at any time after a patient has completed the study and he/she considers there is a reasonable possibility that the event is related to AZD8330, the investigator should notify AstraZeneca, Drug Safety.

Abnormalities in laboratory data

The reporting of protocol mandated laboratory/vital sign abnormalities as both laboratory findings and AEs should be avoided. They should not be reported as AEs unless any criterion for an SAE is fulfilled, the laboratory/vital sign abnormality causes the patient to discontinue treatment with the investigational product (IP) or if the investigator has a strong belief that it should be reported as an AE. All abnormalities from protocol-mandated laboratory/vital measurements will summarised in the Clinical Study Report in the 'Laboratory measurements and variables' section.

If an abnormal laboratory value/vital sign is associated with a diagnosis or clinical signs or symptoms, then the diagnosis, sign or symptom should be reported as an AE and the associated laboratory result/vital sign should be considered additional information to support the diagnosis. This applies to both protocol-mandated measurements and those that are measured outside of protocol requirements.

Disease progression

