6.4.1 Safety Data

Safety data will not be formally analysed. All patients who receive at least one dose of AZD8330 will be included in the assessment of AE profile (evaluable for safety population). Other safety data will be assessed in terms of clinical chemistry, haematology, urinalysis, vital signs, MUGA scan/Echocardiogram, ECGs, ophthalmologic examination, and O₂ saturation. At the end of the study, appropriate summaries of all safety data will be produced, as defined below and in the SAP.

Data from all cycles of initially randomised treatment will be combined in the presentation of safety data. AEs will be listed individually by patient and dose group. For patients who have a dose modification, all AEs (due to drug or otherwise) will be assigned to the initial dose

group. The number of patients experiencing each AE will be summarised MedDRA system organ class (SOC), MedDRA preferred term (PT) and CTC grade. The number and % of patients with adverse events in different categories (e.g. causally related, CTC grade ≥ 3 etc) will be summarised by dose group, and events in each category will be further summarised by MedDRA SOC and PT, by dose group.

Any AE occurring before treatment (ie, before study Day 1) will be included in the data listings but will not be included in the summary tables of adverse events. In addition, a separate data listing of pre-treatment AEs will be produced.

Any AE occurring within 30 days of treatment withdrawal will be included in the AE summaries. Any events in this period that occur after a patient has received further therapy for cancer (following withdrawal of study medication) will be flagged in the data listings. AEs occurring more than 30 days after withdrawal of study medication will be listed separately, but not included in the summaries.

Clinical chemistry, haematology, urinalysis, vital signs, MUGA scan/Echocardiogram, ECGs, ophthalmologic examination, and O₂ saturations will be listed individually by patient and dose group and summarised by treatment dose, as follows:

Haematology, clinical chemistry, vital signs and ECG data will be suitably summarised by dose level for all patients by:

- summary statistics of observed values: mean, standard deviation, minimum, maximum, n
- summary statistics of change from baseline values: mean, standard deviation, minimum, maximum, n

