7.6 Study timetable and end of study

Before a subject's enrolment in the study and any study-related procedures are undertaken the following should be fulfilled:

- Signed Clinical Study Protocol and other agreements between AstraZeneca and the Principal Investigator/Study Site.

- Approval of the study by the Ethics Committee
- Approval of the study, if applicable, by the regulatory authority.

The overall timetable for the study is summarised below:

Study period		Phase of development
Estimated date of first patient enrolled	April 2007	Phase I
Estimated date of last patient completed	August 2010*	

* End of study is defined as the point at which the last patient has received 6 months of treatment with AZD8330, or has withdrawn from the study (whichever is sooner).

In Part A of this study, patients may continue to receive AZD8330 until disease progression or as long as they continue to derive benefit from treatment. Therefore, the time at which the last patient stops treatment cannot be precisely predetermined. The study endpoint is defined as the point at which the last patient has received 6 months of treatment with AZD8330, or has withdrawn from the study (whichever is sooner). The study database will be locked at this point and the Clinical Study Report will be written. Serious adverse event reports for any patients still receiving treatment after the end of study will be entered on the AstraZeneca Global Patient Safety database. The study database will not be updated with this information nor an addendum to the Clinical Study Report be written.

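### Laboratory abnormalities that count as DLTs need not be recorded as adverse events, and the database lock cuts into the 30-day AE window of patients who stopped treatment shortly before it

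*Protocol*

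**What the plan says.** **Recording of laboratory abnormalities.** For protocol-mandated laboratory and vital-sign abnormalities, Protocol Section 4.5.1.2 sets a default of no AE report: "They should not be reported as AEs unless any criterion for an SAE is fulfilled". Two further exceptions follow in the same sentence: the abnormality leads to discontinuation of the study drug, or the investigator strongly believes it should be reported. If a diagnosis, sign or symptom goes with the value, that becomes the AE. DLT status, CTC grade, dose interruption and dose reduction are not exceptions.

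**DLT definition.** Section 3.1.4.2 includes Grade 4 haematological toxicity (neutropenia must last more than 7 days), "Any non-haematological CTC Grade 3 or 4 toxicity despite adequate supportive care", and dose interruptions longer than two weeks.

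**Other significant AEs.** Section 4.5.1.1 describes these as a class of adverse event and says: "Examples of these are marked haematological and other laboratory abnormalities".

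**Safety tables.** Section 6.4.1 tabulates AEs by system organ class, preferred term and CTC grade, with categories such as causally related and Grade 3 or higher. For haematology and chemistry it gives "summary statistics of observed values: mean, standard deviation, minimum, maximum, n", the same statistics for change from baseline, and individual listings that highlight values outside the local reference range.

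**Lock.** Section 7.6 ends the study when the last patient has had 6 months of treatment or has withdrawn from the study, whichever is sooner. It continues: "The study database will be locked at this point and the Clinical Study Report will be written". Section 3.1.2 words the same point as "the point at which the last patient recruited has received 6 months of treatment with AZD8330 or withdrawn from the study". Section 4.5.1.2 collects AEs to 30 days after treatment stops, Table 1 has an AE check 30 days after the last dose, and Section 6.4.1 says: "Any AE occurring within 30 days of treatment withdrawal will be included in the AE summaries".

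**The concern.** Section 4.1 names the incidence and severity of adverse events first among the primary variables. A reader of the study report will judge tolerability by dose from the tables of graded AEs. Two rules can leave those tables incomplete.

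The first lets an event count towards declaring a dose non-tolerated without appearing as an AE. Causality, CTC grade changes and action taken are listed in Section 4.5.1.2 as variables collected for each AE. If no AE is recorded, the protocol names no other place for the judgement that the abnormality was drug-related, although that judgement is part of the DLT definition. A grade can be rebuilt later from the laboratory value; the attribution cannot.

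The second closes the database while part of the promised 30-day window may still be open for patients who have recently stopped treatment.

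The protocol itself expects laboratory toxicity. Section 3.2.2 sets up monitoring for calcium and phosphate changes and for APTT prolongation, and Section 1.1.4 reports raised transaminases with another MEK inhibitor.

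**Working it through.** The plan gives no figure for either effect, so there is none to reproduce. The check compares the rules and then does simple arithmetic.

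**1. Can a laboratory DLT fall outside AE recording?** Take a Grade 3 chemistry value that is judged drug-related, without symptoms and not serious.

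- Section 3.1.4.2: it meets the non-haematological criterion if it occurs within the first 35 days, despite adequate supportive care, and is not clearly due to the underlying disease. No symptom, seriousness or discontinuation is required.
- Section 3.1.4.3: the action at Grade 3 or above is to withhold, with resumption possible after recovery. The discontinuation exception is then not triggered.
- Section 4.5.1.2: no SAE criterion is met and there is no symptom. Only the strong-belief clause is left, and it is discretionary.

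The event can therefore be a DLT without being an AE record.

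**2. Does another stated table count it?** Section 6.4.1 specifies no DLT table and no laboratory table by CTC grade. A cohort mean, SD, minimum and maximum do not give the number of patients at Grade 3 or 4, and the listings flag the local reference range, not the grade.

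**3. Size for the AE tables.** The cut-offs in Section 3.1.4.1 agree with its 25% rule:

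- Non-tolerated: 2/6 = 33.3%, 2/7 = 28.6%, 3/8 = 37.5%, 3/9 = 33.3%; all above 25%.
- Tolerated: 1/6 = 16.7%, 1/7 = 14.3%, 2/8 = 25.0%, 2/9 = 22.2%; none above 25%.

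With k DLTs in n patients, of which j are laboratory-only and unrecorded, the AE table shows (k − j)/n. The documents give no value for j, so the whole range is shown:

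- k = 2, n = 6: j = 0, 1, 2 gives 33.3%, 16.7%, 0%.
- k = 3, n = 9: j = 0, 1, 2, 3 gives 33.3%, 22.2%, 11.1%, 0%.

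Each unrecorded event moves the rate by 1/9 = 11.1 to 1/6 = 16.7 percentage points. In both examples, one is enough to bring the visible rate below 25%.

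**4. Size for the lock.** For a patient who stopped d days before lock, the days of the 30-day window outside the database are max(0, 30 − d). For d = 0, 7, 14, 21 and 30 this gives 30, 23, 16, 9 and 0 days.

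**5. Who is affected by the lock?**

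- When the last patient reaches 6 months and triggers lock, any other patient who stopped in the preceding 30 days is affected.
- When lock is triggered by the last patient's withdrawal, the same holds for other recent stoppers. For the last patient it depends on whether withdrawal from the study means stopping drug or completing the 30-day visit. Section 7.6 does not say.
- Section 3.1.2 refers to the last patient recruited. Read literally, that patient's early withdrawal would end the study while patients recruited shortly before are still short of 6 months.

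**The case against.** Clinical chemistry and haematology are primary variables in their own right. The recording rule has a sensible purpose, to avoid reporting one abnormality twice, and the same paragraph sends all such abnormalities to the laboratory section of the report. With 6 to 9 patients per cohort, individual listings are informative. Section 3.1.4.3 speaks of adverse events when it triggers withholding, so an investigator who judges a Grade 3 or 4 value related and dose-limiting will often hold the strong belief required. Appendix B lists some blood dyscrasias as important medical events, so some haematological DLTs would be reported as SAEs. The sponsor's review for other significant AEs is a further backstop. All of this stands, and it is why the right claim is that such events need not be recorded, not that they will be lost. Asymptomatic chemistry values are the clearest gap.

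A worst-grade table is often left to a SAP. Section 6.1 says none will be prepared because the protocol contains all planned analyses, although Section 6.4.1 refers to one. In any case, a SAP could not recover a causality judgement that was never collected.

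A reader might infer that escalation decisions or the MTD are compromised. The documents do not support that: the Safety Review Committee reviews DLTs and all safety assessments to Day 35 (Section 3.1.4.1), and the events that defined the MTD were mental-status changes reported as adverse events (Section 1.1.3).

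On the lock, patients still on treatment meet a disclosed administrative cut-off, with later SAEs going to the safety database. The tail at issue is small and will mostly lie well beyond the 35-day DLT window. A reader might infer that the last patient's 30 days are always lost; under the withdrawal branch this is not established, because the term is undefined.

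**Conclusion.** Both points hold in limited form.

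- **AE tables.** A non-serious, asymptomatic laboratory abnormality that meets a DLT criterion and is managed without discontinuation need not become an AE. The AE-by-grade tables can then under-count toxicity by 11 to 17 percentage points per event in a cohort of 6 to 9. A non-tolerated cohort showing 0/6 is possible under the rules, but it needs every DLT to be of this kind and unrecorded. It is an illustration, not an expectation. It would be too strong to say that the toxicity disappears from the report: the values are still listed and summarised, but no stated table counts patients by laboratory grade.
- **Lock.** Section 7.6 conflicts with Sections 4.5.1.2 and 6.4.1 for patients who stopped in the 30 days before lock. Each loses 30 − d days of AE follow-up. The number of such patients cannot be derived from the documents.

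The defect is in the completeness of the reported dose-toxicity record. It is worth correcting because AE incidence and severity is primary and the correction is cheap.

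**What to change.** **Section 4.5.1.2.** Add that any laboratory or vital-sign abnormality classed as a DLT, or leading to dose interruption or reduction, is recorded as an AE with its CTC grade and causality. This also brings the section into line with Sections 3.1.4.2 and 4.5.1.1. No DLT criterion or dosing rule changes.

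**Section 6.4.1.** Add baseline-to-worst CTC grade tables for haematology and chemistry by dose group.

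**Sections 3.1.2 and 7.6.** Reconcile them with Sections 4.5.1.2 and 6.4.1:

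- Set the data cut-off when all patients have had 6 months of treatment or have withdrawn.
- Lock only after the 30-day follow-up of patients who stopped by that cut-off.
- State that patients still on treatment are censored at the cut-off, with later SAEs going to the safety database. Without this, waiting for everyone's 30-day visit could delay lock indefinitely, because the protocol allows treatment beyond 6 months.

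**Cost.** Amendment wording, a few more AE records, one set of standard tables, and a lock about 30 days after the cut-off.

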4.5.1.3 Reporting of serious adverse events

Investigators and other site personnel must inform appropriate AstraZeneca representatives of any SAE that occurs in the course of the study within 1 day (ie, immediately but no later than the end of the next business day) of when he or she becomes aware of it.

Follow-up information on SAEs must also be reported by the investigator within the same time frames.

If a non-serious AE becomes serious, this and other relevant follow-up information must also be provided to AstraZeneca within 1 day as described above. For a non-serious AE that become serious but which is not fatal or life threatening a report should be received within 5 days.

The AstraZeneca representative will work with the investigator to compile all the necessary information and ensure that the appropriate AstraZeneca Drug Safety Department receives a report by day 1 for all fatal and life-threatening cases and by day 5 for all other SAEs.

4.5.2 Laboratory safety measurements and variables

4.5.2.1 Methods of assessment

The following clinical chemistry, urinalysis and haematology tests will be performed:

Clinical chemistry	Haematology
s - Albumin	B - Erythrocyte count
s - Alanine aminotransferase (ALT)	B - Haemoglobin
s - Aspartate aminotransferase (AST)	B - Platelet count
s - Alkaline phosphatase (ALP)	B - Leucocyte cell count
s - Total Calcium	B - Leucocyte differential count (absolute count):
s - Creatinine	B - Monocytes,
s - Gamma glutamyltransferase (γGT)	B - Neutrophils,
s - Glucose	B - Lymphocytes,
s - Magnesium	B - Basophils
s - Phosphate	B - Eosinophils
s - Potassium	B/p - Activated Partial Thromboplastin Time (APTT)
s - sodium	B/p-Prothrombin Time (PT)
s - Total protein	B-Thrombin Time (TT)
s - Total bilirubin	
s - Urea nitrogen	
s/p - BNP or NT-proBNP	
s-Troponin T (or Troponin I)	
Urinalysis	
U-Glucose	U-Blood
U-Protein	U-Microscopy (red blood cells and white blood cells, bacteria, casts and crystals) only perform if urinalysis abnormal

An unscheduled serum urea and creatinine test should be performed in every case of an SAE of diarrhoea. In addition, clinical chemistry, haematology, coagulation and urinalysis testing will be repeated as clinically indicated as part of the routine management of the patient on the occurrence of AEs.

Adjusted Calcium will be calculated using for formula below, from Total Calcium and Albumin:

$$\text{Adj. Calcium} = \text{Total Calcium (mmol/L)} + ([40 - \text{Albumin (G/L)}] \times 0.02)$$

4.5.3 Vital signs, ECG and physical examination

4.5.3.1 Vital signs

Resting supine blood pressure and pulse rate will be measured using a semi-automatic blood pressure recording device with an appropriate cuff size. See study plan [Table 1](#) for time points.

Any symptoms from the patient should if applicable be registered as an AE.

4.5.3.2 ECG

(a) Screening (all patients)

All patients participating in the study will have a screening ECG. Patients will be excluded from the study if a QTc is >450 ms. The screening ECG will be analysed locally. The screening assessment can be conducted within 48 hours of visit 1.

(b) Treatment Phase ECGs

Patients receiving AZD8330 will have 12-lead ECGs captured in triplicate pre-dose, 1 hour 30 minutes and 4 hours post-dose on Visit 2 (Day 1), and Day 15. In addition ECGs performed in triplicate at withdrawal from treatment, any cardiac event with symptoms due to cardiac ischemia (such as chest pain, or any arrhythmia (such as palpitations), and in cases of dyspnoea and pulmonary oedema.

All ECGs (with the exception of screening ECGs) will be transmitted electronically for central reading and interpretation by an AstraZeneca appointed external cardiologist. Details of recording and transmission of ECGs are provided in the study specific ECG manual provided to investigators. Parameters including QRS duration, R-R, PQ, and QTc will be determined and reviewed by an external cardiologist. Pulse rate and QTcF, will be calculated by AstraZeneca from the data provided by the external cardiologist.

Patients who continue to receive treatment beyond the defined end of study, in accordance with Section 7.6 (Study timetable and end of study) will no longer have ECGs analysed by an external cardiologist, but should continue to be reviewed by site staff as per routine practice.

The Investigator should review the paper copy of the ECGs on each study day and may refer to a local cardiologist if appropriate.

Any symptoms from the patient should be registered as a comment and if AE criteria are met, recorded as an AE.

